patient compliance. The medications must be applied up to two times a day for as long as 2-12 months. Another limitation is limited penetration into the affected part of the nail unit. The therapies are not effective on all nail changes associated with nail psoriasis, and may have poor absorption into the parts of the nail unit responsible for different features of the disease. Systemic therapies such as acitretin, cyclosporin A, and methotrexate are also sometimes used. Good results have been reported with the use of systemics, though they also require strict patient compliance. Biologic drugs such as alefacept, etanercept, infliximab are newer therapies in the treatment of nail psoriasis. They too, have shown to be effective, though confer a risk of severe immunosuppression.

Intralesional corticosteroids, most commonly triamcinolone acetonide (ITA), are often used in the treatment of nail psoriasis. TA is a corticosteroid that is FDA approved for the treatment of psoriasis via intralesional injection. Corticosteroids are used in the treatment of many inflammatory dermatologic diseases. Briefly, they work by inhibiting the body's inflammatory response. At higher doses, the response is more inhibited.

ITA is used in concentrations ranging from 2.5mg/mL - 10mg/mL in the treatment of nail psoriasis.[1, 3] There is debate in the literature regarding the ideal concentration of ITA to treat nail psoriasis.[1] That is, the dose that gives the best efficacy while limiting side effects. No randomized prospective studies investigating this question exist. A number of authors have conducted studies on the efficacy of ITA in the treatment of nail psoriasis using specific concentrations of ITA (most commonly 5mg/mL or 10mg/mL). [6-10] To our knowledge, no authors have directly compared the concentrations to one another. Determining the lowest effective concentration of ITA is important because patients receiving higher than necessary concentrations may experience an increase in side effects. The side effects of corticosteroids such as TA are numerous, and include thinning of the skin at the site of injection, thinning along the lymphatic vessels draining the injection site, allergic reactions, infection, and pituitary suppression.[11]

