Another secondary objective is to determine the rate and nature of side effects experienced by patients using different concentrations of intralesional triamcinolone acetonide for the treatment of nail psoriasis.

Another secondary objective is to assess baseline quality of life in patients with nail psoriasis and determine if there is a change in quality of life with the study intervention.

SUBJECT POPULATION

Inclusion Criteria:

The subject must meet ALL the criteria listed below for entry:

1. Subject must be at least 18 years of age, of either sex or transgendered individuals, and of any race;
2. Subject must have nail psoriasis that is clinically diagnosed of at least 2 fingernails.
3. Subject must be willing to give written informed consent and able to adhere to procedures and visit schedules;
4. Subject must consent to having the fingernails photographed during the study period

Exclusion Criteria:

The subject will be excluded from entry if ANY of the criteria listed below are met:

1. Subject with any clinically significant condition or situation, other than the condition being studied that, in the opinion of the investigator, would interfere with study evaluations or optimal participation in the study. This is including, but not limited to: immunodeficiency, onychomycosis, any other nail condition other than psoriasis, allergy to triamcinolone acetonide, local anesthetic, normal saline, or any other material used for procedures.
2. Subject who has received radiation therapy, chemotherapy, and/or immunosuppressive drugs within 6 months of study, and/or oral corticosteroids for >1 month within the 6 months of study (exception: inhaled steroids);
3. Subject known to have received treatment with investigational drugs or devices within 30 days prior to enrollment into this study;
4. Subject who is unwilling to abstain from any cosmetic nail treatments outside those provided by the study clinic, beyond basic nail trimming (i.e. no spa nail treatments, no nail polish use, no other topical prescription nail medication);

5. Subject who is unwilling to abstain from any medical nail treatments on their nails other than the study intervention (i.e. topical steroids, antifungal creams) for the duration of the study intervention and for duration of the washout period (if applicable);
6. Subject who is part of the staff personnel directly involved with this study or a family member of the investigational study staff

CONCOMITANT MEDICATIONS

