All concomitant medication usage from the period of 60 days prior to the trial through the trial period shall be documented and include the following information:

1. Medication
2. Indication
3. Dosage (including frequency)
4. Start / Stop date

All concomitant medication usage will be checked with respect to exclusion criteria and cross-referenced to adverse events (if any).

RESEARCH DESIGN / METHODS

Our approach is to assess the efficacy and safety of different concentrations of ITA in the treatment of nail psoriasis. A similar approach has been taken with psoriasis of the skin, and alopecia areata.[15, 16]

Hypothesis: The lowest concentration of ITA tested offers the best ratio of efficacy to safety.

Study Design: A total of 10 subjects who have nail psoriasis of at least two fingernails will be enrolled. During the screening visit, the investigator will discuss with each subject the nature of the study, its requirements and its restrictions during the Informed Consent Process.

The following will be performed at the screening visit:

- Review of inclusion/exclusion criteria
- Medical history and demographics including age, gender, history of psoriasis
- Review of medications
- Examination of the fingernails
- Possible tissue sampling (clipping the nail) to rule out onychomycosis
- X-ray of the affected hand
- Administration of a survey assessing quality of life at baseline.
- Use the study intervention (intralesional triamcinolone acetonide injections) on your fingernail(s)

Eliciting the patient history and physical exam are part of standard clinical practice.

Nail psoriasis is a clinical diagnosis. Tissue sampling may be taken if there is a question about diagnosis, or if there is a possible confounding diagnosis such as onychomycosis. X-rays of the hand may also be taken to determine if there is co-existing arthritic involvement, which is very common in nail psoriasis. Both of these events are part of standard clinical practice and are not research-related procedures. Patients who only decline to obtain x-rays won't be excluded from the study.

After completion of the informed consent process, the study site will take photos of the affected fingernails proposed for enrollment.

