Washout Period: Subjects who are using any form of treatment on their nails at the time of the screening visit may participate in the study provided that they are willing to undergo a two-month washout period. During this time, they must abstain from using any nail treatments (including, but not limited to: spa nail treatments, nail polish use, prescribed topical or systemic medications indicated for the nails, over the counter nail treatments, or any other nail intervention with the exception of routine clipping and washing.) After the washout period, the subject may be re-evaluated for participation in the study.

Enrollment and Randomization: Patients with at least two affected fingernails will be enrolled. For each participant, one fingernail will receive an intralesional injection of 0.1-0.2 mL of normal saline (placebo). The other affected fingernail(s) will receive an injection of 0.1-0.2mL of a pre-determined concentration of ITA. Four concentrations of ITA will correspond to four study groups: 2.5mg/mL, 5mg/mL, 7.5mg/mL and 10mg/mL. Participants' fingernails will be randomized such that there are approximately equal numbers of fingernails in each of the five groups (four study interventions, one placebo). To avoid bias, fingernails will be assigned to groups systematically. Fingernails will be assigned to groups in order of anatomical convention. For example, if the subject has involvement of both the thumb, forefinger and third finger of the right hand, the thumb is the first digit, so, if involved, it will be assigned first according to the table below. If a subject has involvement of fingernails of both the right and left hand, the fingernails of the right hand will be assigned before the left. The table assumes that up to 50 nails will be affected between the 10 subjects enrolled. In our clinical experience, this is a reasonable expectation. If more or fewer fingernails are involved during the enrollment period, the randomization table will be adjusted accordingly. The concentration of ITA injected will be different for each group. All other study procedures will be the same between groups.

Fingernail	Group
1	5
2	3
3	4
4	1
5	2
6	4
7	5
8	1
9	3
10	2
11	3
12	4
13	5
14	1
15	2

16	2
17	1
18	3
19	5
20	4
21	5
22	4
23	3
24	2
25	1
26	1
27	2
28	3
29	4
30	5
31	1
32	2
33	4
34	3
35	5
36	5
37	3
38	4
39	2
40	1
41	1
42	3
43	4
44	2
45	5
46	1
47	5
48	2
49	4
50	3

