Table 1: Randomization of subjects' fingernails to groups. Groups are numbered 1-5 and correspond to concentrations of ITA such that 1=2.5mg/mL; 2=5.0mg/mL; 3=7.5mg/mL; 4=10.0mg/mL; 5=placebo.

Procedures: Injections of ITA will be administered using standard methods. Hand hygiene procedures will be performed and the administrator will use gloves. Triamcinolone acetonide, at the determined dose, will be drawn into a solution of 1% lidocaine. The nail fold of the affected nail will be cleaned with an alcohol swab. In addition to the local anesthetic given as part of the injection, the area will be anesthetized with an ethyl chloride spray immediately prior to injection using a 30 gauge needle. During injection, the participant may experience light pressure. Following injection, the wound will be covered with a bandage. A board-certified dermatologist will perform all procedures and will be present to monitor for unlikely adverse events, such as excessive bleeding.

None of these procedures differ from the current standard of care. The only aspect that will differ in the treatment of affected nails is the concentration of ITA used. However, there is no current standard of care regarding the concentration; all concentrations under investigation are part of typical clinical practice and have been validated in studies.[1] The purpose of this study is to determine the lowest effective concentration of ITA in the treatment of nail psoriasis.

The schedule of treatments is as follows:

Treatment will be performed using ITA with a frequency of once per 6 weeks +/- 1 week. A follow-up visit will be performed at 24 weeks, ending the study period.

The following will be performed at the first visit:

- Completion of Nail Psoriasis Severity Index
- Collection of survey to document subject's quality of life
- Use the study intervention (intralesional triamcinolone acetonide injections) on the subject's fingernail(s)
- Take pictures of subject's nails before and possibly after treatment
- Take an X-ray of the affected hand

The following procedures will be performed at every treatment visit after the first, and at the follow-up visit:

- Measurements of clear nail growth (in millimeters), clear nail area (in mm²)
- Completion of Nail Psoriasis Severity Index.
- Use the study intervention (intralesional triamcinolone acetonide injections) on the subject's fingernail(s)
- Take pictures of subject's nails before and possibly after treatment

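### The two-month washout depends on nail treatment being in use at screening, not on time since last use, so a subject who has just stopped can be injected with no washout

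*Combined protocol and SAP*

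**What the plan says.** **Washout Period (Research Design / Methods).** Two months of abstention is the condition of entry for "Subjects who are using any form of treatment on their nails at the time of the screening visit". The list of barred treatments is broad: cosmetic, prescribed topical or systemic, over-the-counter, and anything else beyond clipping and washing. The subject is then reassessed for entry.

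**Exclusion Criteria (Subject Population).** Criterion 2 looks back over "immunosuppressive drugs within 6 months of study, and/or oral corticosteroids for >1 month within the 6 months of study", and also covers radiation and chemotherapy. Criterion 3 looks back 30 days for investigational products. Criteria 4 and 5 concern unwillingness to abstain. The medical-treatment one, criterion 5, applies "for the duration of the study intervention and for duration of the washout period (if applicable"). Criterion 1 leaves interfering conditions or situations to the investigator's opinion.

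**Concomitant Medications.** Medications are logged from 60 days before the trial, with indication and start and stop dates. "All concomitant medication usage will be checked with respect to exclusion criteria".

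**Timing of the first injection.** The screening-visit list includes this item: "Use the study intervention (intralesional triamcinolone acetonide injections) on your fingernail(s"). The Procedures paragraph lists the injection again for a first visit. No minimum gap between the two visits is stated.

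**Context.** The Introduction/Background says: "Intralesional corticosteroids, most commonly triamcinolone acetonide (ITA), are often used in the treatment of nail psoriasis". The treatment schedule says: "Treatment will be performed using ITA with a frequency of once per 6 weeks +/- 1 week".

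**The concern.** The sponsor has judged that a nail under treatment needs two months to settle before study entry. That reasoning concerns time since last exposure, but the rule is attached to status on one day. Someone who stopped a topical steroid yesterday and someone who will stop it today are nearly the same biologically, yet only the second must wait.

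Efficacy is judged on clear-nail growth and area and on NaPSI, each set against baseline. If a recently treated nail is still improving, or is relapsing after withdrawal, its baseline is unsettled and its change score mixes the old treatment with the new. Earlier triamcinolone is a particular case because it is the study drug. The Background makes prior use plausible, and a recent injection could mean that the saline nail is not drug-free when the trial begins. Both the comparison with saline and the comparison among concentrations depend on those nails.

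**Working it through.** The plan gives no calculated figure to reproduce. The check reads the washout trigger against every other rule that might catch a recent stopper, then compares the shortest interval each type of subject can have.

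**Step 1. Does another rule close the gap?**

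- Criterion 2: no. It treats corticosteroids separately from immunosuppressive drugs and names only the oral route.
- Criterion 3: no. It covers investigational products only.
- Criteria 4 and 5: no. They look forward, and criterion 5 mentions the washout only where one applies.
- Criterion 1: only at the investigator's discretion. It gives no window and does not mention earlier nail treatment.
- Medication log: it would show a recent drug, but it is checked against exclusion criteria, none of which covers this case.

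**Step 2. Shortest interval from last nail treatment to first study injection.**

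- In use at screening: two months, about 60 days.
- Stopped the day before screening and injected at screening: about 1 day.
- Difference: 60 − 1 = about 59 days, for subjects whose last use differs by a day.
- Course of triamcinolone completed four weeks before screening: 4 × 7 = 28 days. The study's own interval is 6 weeks ± 1 week, that is 35 to 49 days. The study injection could therefore come sooner after the old one than the plan allows between two of its own.

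**Step 3. Does comparison with the saline nail remove the problem?** Only partly. If all of a subject's nails had the same earlier treatment and effects add, a shared residual cancels in the within-subject difference. If only some nails were treated before, it does not. A subject may enter with two affected nails, one of them saline, and so contributes only one concentration. Comparisons among concentrations are then partly between subjects.

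**Step 4. How often?** The documents give no rate. As illustration only, suppose a share p of candidates stopped within two months. The chance that at least one of 10 subjects is affected is 1 − (1 − p)^10:

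- p = 0.05: 1 − 0.95^10 = 40%
- p = 0.10: 1 − 0.90^10 = 65%
- p = 0.20: 1 − 0.80^10 = 89%

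These rates have no source, and p = 0 is equally compatible with the plan. One subject is 1/10 = 10% of subjects, but allocation is by nail: a two-nail subject is 2/50 = 4% of the nails in the allocation table.

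**Step 5. Can the 60-day log support a two-month rule?** Nearly. Two average months are 2 × 365.25/12 = 60.9 days, so the log falls about a day short. It also records medications only, whereas the washout list includes polish and spa treatments.

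**The case against.** The strongest defence is that the gap is narrow and partly guarded. An investigator could fairly say that a patient injected four weeks ago, midway through a course, is still using treatment and so must wash out. That stands: the clear gap is confined to subjects who have finished or quit. Criterion 1 and the medication review also give a careful investigator grounds to act. That stands too, but it leaves eligibility to judgement where the plan already has a rule for nearly identical subjects.

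A reader might infer three stronger things, which the documents do not support.

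- **That the dose comparison is compressed by a known amount.** Assume four study injections of equal volume. A 2.5 mg/mL course is then 4 × 2.5 = 10 units and a 10 mg/mL course is 4 × 10 = 40, a ratio of 4.0. One earlier injection within the Background's range ("ITA is used in concentrations ranging from 2.5mg/mL - 10mg/mL in the treatment of nail psoriasis") changes this to 42.5/12.5 = 3.4 at the low end and 50/20 = 2.5 at the high end. These figures are illustrative upper limits on exposure, with the old dose counted in full, and are not effects. Volume may vary from 0.1 to 0.2 mL. Four injections is itself an inference, because one visit list includes the injection at follow-up. Bias in the difference from saline also requires unequal earlier treatment or non-additive response.
- **That old nail plate carries through to the end.** Under linear growth with 4.35 weeks per month, a six-month nail takes 6 × 4.35 = 26.1 weeks. With treatment stopped one week before baseline, (26.1 − 1 − 24)/26.1 = 4% is old plate at week 24. With four weeks, none is. A four-month nail (17.4 weeks) has none in either case.
- **That the two-month washout clears all nail quadrants of old plate and a shorter gap does not.** In a six-month nail the proximal half takes 13.05 weeks to grow. After 8.7 weeks of washout, (13.05 − 8.7)/13.05 = 33% of that half is still old. Old plate also need not be improved plate.

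**Conclusion.** The point holds as a fault in the trigger of a stated rule. A subject who has finished or quit topical or intralesional nail treatment shortly before screening can be injected with no washout, although the plan requires two months of a current user. The minimum interval is about 1 day against about 60 days, given that injection at the screening visit is permitted as listed.

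The consequence is a possible distortion of baseline NaPSI and clear-nail measurements, and possible active drug in the saline nail. The direction is uncertain, since residual benefit and relapse pull opposite ways. Neither frequency nor size can be calculated from the documents, and it may be that no subject is affected. The point therefore does not show that the trial's comparisons are biased. It is a cheap improvement of modest importance, worth making because each subject is a tenth of the trial.

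**What to change.** Keep the two-month length and count it from last use. Suggested wording for the Washout Period paragraph:

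*No nail treatment of the kinds listed in this section, including intralesional injection, within two months before the first study injection. A subject with such treatment waits until two months have passed since last use and is then re-evaluated.*

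Confirm this before the first injection in two ways. For drugs, use the medication log, lengthened from 60 days to two months and counted back from the first study injection. For non-drug nail treatments, add a question to the screening history. An injection at the screening visit should go ahead only once both are clear. No change to the analysis is needed.

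The cost is a short text change, a slightly longer log and one history question. Recent stoppers are delayed by up to two months without nail treatment, as current users already are, and some may decline, which could slow recruitment of the 10 subjects.

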Our study will enroll participants with at least two fingernails involved. This will allow us to use placebo in one fingernail of every participant, thus establishing the efficacy of ITA in our study by allowing us to compare placebo to ITA. In addition to efficacy assessments, we will measure changes in quality of life due to the study intervention as an outcome. Quality of life assessments will be done with the NPQ10 assessment, which is a validated assessment tool developed to measure quality of life in nail psoriasis.[14] This tool is included in Appendix B.

All fingernails not treated with placebo will undergo randomization to four groups corresponding to four concentrations of ITA under investigation (2.5, 5.0, 7.5, 10.0 mg/mL). Thus, a participant with five affected fingernails may have a different concentration of ITA used as the study intervention in each fingernail. This approach has been used in studies of ITA in other dermatologic diseases such as alopecia areata. [15] In the cited study, the lesions of subjects with alopecia areata were divided into four quadrants, corresponding to four concentrations of ITA that were injected. We believe this approach will be helpful in comparing the efficacy of different concentrations in the same patient.

SIGNIFICANCE

Psoriasis is a chronic, inflammatory condition that affects millions of people in the United States. Approximately 50% of patients with cutaneous psoriasis have nail involvement; nail psoriasis causes significant pain, and can lead to loss of manual dexterity, therefore impairing the ability to use the hands or perform work. Intralesional triamcinolone acetonide is considered one of the mainstays of treatment for nail psoriasis. By determining the lowest effective concentration of this medication for nail psoriasis, we can minimize side effects for millions of people affected with nail psoriasis worldwide.

OBJECTIVES

The primary objective of this study is to determine the lowest effective concentration of intralesional triamcinolone acetonide in the treatment of nail psoriasis.

The secondary objective is to determine that intralesional triamcinolone acetonide is effective in the treatment of nail psoriasis when compared to placebo, using the Nail Psoriasis Severity Index as a measure of improvement.

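### One placebo nail is promised in every participant, but the five-group running list has no rule that delivers it; at 46 or fewer nails in total, at least one of 10 participants gets none

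*Combined protocol and SAP*

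**What the plan says.** Two allocation schemes are described.

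**Scheme A: placebo set apart within each participant.** The Introduction says of the two-nail entry requirement: "This will allow us to use placebo in one fingernail of every participant, thus establishing the efficacy of ITA in our study". It continues: "All fingernails not treated with placebo will undergo randomization to four groups corresponding to four concentrations of ITA under investigation". Enrollment and Randomization repeats the promise, "For each participant, one fingernail will receive an intralesional injection of 0.1-0.2 mL of normal saline (placebo", and adds: "The other affected fingernail(s) will receive an injection of 0.1-0.2mL of a pre-determined concentration of ITA".

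**Scheme B: one five-group list over all nails.** The same section says that "fingernails will be randomized such that there are approximately equal numbers of fingernails in each of the five groups", four active and one placebo. It also says: "Fingernails will be assigned to groups in order of anatomical convention", right hand before left. Each nail takes the next row of Table 1, a 50-row list meant to cover the nails of all 10 participants together. The caption codes placebo as group 5. If the nail total differs, the table is to be adjusted; no method is given.

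Two other statements bear on this. Inclusion criterion 2 reads: "Subject must have nail psoriasis that is clinically diagnosed of at least 2 fingernails". The first secondary objective reads: "The secondary objective is to determine that intralesional triamcinolone acetonide is effective in the treatment of nail psoriasis when compared to placebo", measured by the Nail Psoriasis Severity Index.

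**The concern.** Staff cannot in general follow both schemes. Scheme A fixes 10 placebo nails, one per person. Scheme B fixes about a fifth of all nails as placebo, wherever they fall. Nothing says which nail is the placebo nail, or what to do when a participant's rows contain no placebo or two.

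If the list is followed as printed, some participants have no placebo nail. They drop out of any within-participant comparison of triamcinolone with placebo. Their active nails could still enter an unpaired comparison, but the plan gives the per-participant placebo as the means of establishing efficacy. If staff depart from the list to keep the promise, they make unscripted allocation decisions during enrollment.

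**Working it through.** **Inputs.** 10 participants (Study Design); at least two affected nails each (Inclusion criterion 2); the 50 printed rows and group codes (Table 1). The list is taken to run on from one participant to the next, the plain reading of a 50-nail table for 10 subjects together.

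**1. The plan's own figure.** The table has 50 rows, 10 per group, in ten consecutive blocks of five that each hold every group once. So there are 10 placebo rows for 10 participants, and with exactly five nails each everyone gets exactly one.

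**2. The threshold.** Placebo rows are 1, 7, 13, 19, 21, 30, 35, 36, 45 and 47. Let P(N) be the number of placebo rows among the first N. At least 10 − P(N) participants have no placebo nail, however the nails are spread.

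| Total nails N | P(N) | At least this many without placebo |
|---|---|---|
| 20 | 4 | 6 |
| 30 | 6 | 4 |
| 40 | 8 | 2 |
| 46 | 9 | 1 |
| 47 | 10 | 0 |

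**3. Equal nail counts.**

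| Nails each | Placebo nails, participants 1 to 10 | With none | With two |
|---|---|---|---|
| 2 | 1,0,0,1,0,0,1,0,0,1 | 6 | 0 |
| 3 | 1,0,1,0,1,0,2,0,0,1 | 5 | 1 |
| 4 | 1,1,0,1,1,1,0,1,2,0 | 3 | 1 |
| 5 | all 1 | 0 | 0 |

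**4. Reaching 47 nails is not enough.** Among all ordered splits with 2 to 10 nails per participant, those giving everyone a placebo nail number 66,010 of 49,462,810 at N = 47 (0.13%) and 141,450 of 82,044,082 at N = 50 (0.17%). The highest share from 47 to 50 is 0.24%, at 48. These are shares of possible splits, not probabilities.

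**5. Local features of the list.** Rows 22–29 and 37–44 contain no placebo, so a participant with as many as eight nails can miss it. Rows 35 and 36 are both placebo, so a two-nail participant there would get placebo twice and no active injection. Over all runs of k consecutive rows, the number with no placebo is 31 of 49 for k = 2, 24 of 48 for k = 3, 17 of 47 for k = 4, 11 of 46 for k = 5 and 6 of 45 for k = 6. These weight every start row equally and are not probabilities either.

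**6. Precision.** Assume independent nail errors of equal variance within a participant. A participant with a active and p placebo nails contributes information a·p/(a+p) to the pooled within-participant contrast.

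- 2 nails each: printed list 4 × 1/2 = 2.0; one placebo each 10 × 1/2 = 5.0. Standard error ratio √(5.0/2.0) = 1.58.
- 3 nails each: 5 × 2/3 = 3.33 against 10 × 2/3 = 6.67. Ratio √(6.67/3.33) = 1.41.
- 4 nails each: 6 × 3/4 + 1 × 1 = 5.5 against 10 × 3/4 = 7.5. Ratio √(7.5/5.5) = 1.17.

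For an unpaired comparison of all active with all placebo nails, treating nails as independent, the same formula on the totals gives √(5/3.2) = 1.25, √(6.67/4.8) = 1.18 and √(7.5/6.4) = 1.08.

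**7. The two promises against each other.** One placebo nail each leaves (N − 10)/4 per concentration. This equals 10 only at N = 50. Against 10 placebo nails, each concentration has 8.75 at 45 nails, 7.5 at 40, 5 at 30, 2.5 at 20 and 12.5 at 60.

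**The case against.** **Block i might belong to participant i.** The ten blocks of five suit such a reading. The placebo then sits at positions 1, 2, 3, 4, 1, 5, 5, 1, 5 and 2 of the blocks. With at least two nails each, everyone could have a placebo nail with as few as 2+2+3+4+2+5+5+2+5+2 = 32 nails. The threshold of 46, the eight-row gaps and the double placebo at rows 35–36 would disappear. But the text does not say this, participants with 2, 3 or 4 nails each would still leave 5, 4 and 3 people without placebo, and a sixth nail would have no row. Restarting at row 1 for each participant would secure a placebo nail but leave rows 11–50 unused. So the 46-nail figure depends on the running-list reading; the defect does not.

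**The protocol directs one placebo nail each and allows the table to be adjusted.** This is the strongest point. Staff who noticed could repair the list, so the counts above are what the printed list gives, not a forecast. But adjustment is triggered by the nail total, not by a missing placebo. It has no method, and the total is known only after earlier nails have been assigned.

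**No paired test is specified.** True. The 1.58, 1.41 and 1.17 ratios apply only to a within-participant contrast; the unpaired losses are smaller.

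**The remedy reaches past the defect.** In part. The minimum is a rule for picking the placebo nail and a four-group list for the rest. Concealment adds protection, since the whole list is printed in the protocol. Some random choice of the placebo nail is needed, because a fixed anatomical choice would tie placebo to a particular finger.

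**Conclusion.** The concern holds and should be settled before any nail is assigned. The Introduction and the Enrollment and Randomization section promise a within-person placebo control that the printed list does not secure. On the running-list reading, the promise must fail for at least one participant at 46 or fewer nails, and it fails for nearly all uneven splits at 47 to 50. With 2, 3 or 4 nails each, 6, 5 and 3 of 10 participants have no control. The standard error inflation of 1.58, 1.41 and 1.17 further assumes independent, equal-variance nail errors and a within-participant analysis. Separately, and on any reading of the list, one placebo nail each is compatible with five about equal groups only near 50 nails.

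**What to change.** Reconcile the Introduction, Enrollment and Randomization, and Table 1 so that one rule governs:

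1. In each participant, list all affected nails before any assignment is revealed and put them in random order.
2. The first nail in that order receives placebo.
3. The remaining nails take the next rows of a concealed, computer-generated list of the four existing concentrations, for example in permuted blocks of four. Concentration totals then differ by at most one nail.
4. Remove group 5 from the running table. Replace the anatomical-order rule and the adjustment clause with a statement that the four-group list is long enough for any total.
5. Replace the statement of five about equal groups with 10 placebo nails and about (N − 10)/4 nails per concentration.

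A rule against repeating a concentration within a participant is optional.

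**Cost.** A protocol amendment and a new list; no extra patients, visits or staff. Below 50 nails, the concentrations that the primary objective compares have fewer nails than under an equal five-way split: 8.75 rather than 9 at 45 nails, 7.5 rather than 8 at 40, 5 rather than 6 at 30, and 2.5 rather than 4 at 20. Treating nails as independent, the standard error between two concentrations rises by √(8/7.5) = 1.03 at 40 nails, √(6/5) = 1.10 at 30 and √(4/2.5) = 1.26 at 20. Someone who has seen the earlier assignments could work out the last concentration in a block of four; the random nail order hides which nail gets it unless only one active nail remains.
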